### **Ethical Consideration**

- Agreement for this study will be obtained from the hospital's ethical committee.
- Study protocol will be submitted for approval by IRB.
- Informed consent will be obtained from pregnant women after adequate provision of information regarding the study requirements and purpose.
- Personal privacy will be respected in all levels of the study. Collected data will not be used for any other purpose.

### **Statistical analysis**

Data will be entered and analyzed using IBM-SPSS software (IBM Corp. Released 2017. IBM SPSS Statistics for Windows, Version 25.0. Armonk, NY: IBM Corp.)

Qualitative data will be presented as Number and percent, Quantitative data will be tested for normality using Shapiro-Wilk's test then described as mean and standard deviation for normally distributed data and median and range for non-normally distributed. The appropriate statistical test will be applied according to data type with the following suggested tests: Chi-Square for categorical variable.

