### **Aim of work**

This study to evaluate the effect of advanced maternal age on the outcomes of pregnancy which include: maternal, obstetric, fetal and perinatal outcomes.

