## Sample size

Sample size was calculated by PASS 15 Power Analysis and Sample Size Software (2017). NCSS, LLC. Kaysville, Utah, USA, [ncss.com/software/pass](http://ncss.com/software/pass).

Based on previous studies including Yogev et al. (2010), the authors hypothesize an overall poor outcome in 20% of young pregnant group vs. 60% in elderly pregnant group with a prevalence of elderly pregnant ladies of 25% vs. 75% of young pregnant ladies.

A logistic regression of a binary response variable (Y) on a binary independent variable (X) with a sample size (N) of 80 observations (of which 50% are in the group X=0 [40 young pregnant ladies] and 50% are in the group X=1 [40 elderly pregnant ladies]) achieves 94% power at a 0.050 significance level to detect a change in Prob (Y=1) from the baseline value of 0.200 to 0.600. This change corresponds to an odds ratio of 6.000. A two-sided Wald test is used.

Considering a possible dropout rate (DR) of 20%, the expected number of dropouts will be 20, and the dropout-inflated enrollment sample size (N') will be 100 participants (50 young, and 50 elderly) where  $N' = N / (1 - DR)$ .

- We will have 2 groups: the **first** group will be represented by 50 women aged 35 y or more and the **second** group will be represented by 50 women aged from 20 to 34 y.
- **The first group** will be also divided into 2 subgroups: group (1A) aged from 35y to 40 y, the group (1B) aged above 40 y and we will compare between the outcomes in the 2 groups which include maternal, obstetric, fetal and perinatal outcomes.
- We will also compare between those with spontaneous pregnancy and those with ART.

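### No effect estimate or confidence interval is planned for categorical outcomes, so for uncommon outcomes a non-significant chi-square would not show which increases in risk remain possible

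*Combined protocol and SAP*

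**What the plan says.** The Aim of work section sets an effect question: "This study to evaluate the effect of advanced maternal age on the outcomes of pregnancy".

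The Statistical analysis section states how results will be shown. For categorical outcomes: "Qualitative data will be presented as Number and percent". For quantitative data, after a Shapiro-Wilk test: "described as mean and standard deviation for normally distributed data and median and range for non-normally distributed". On testing: "The appropriate statistical test will be applied according to data type with the following suggested tests: Chi-Square for categorical variable". The section names no risk difference, risk ratio, odds ratio or confidence interval for any outcome.

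The Sample size section rests on a logistic regression of a binary outcome on age group. With 80 evaluable women, 40 per group, it "achieves 94% power at a 0.050 significance level" for a change from 20% to 60%, an odds ratio of 6.0, by a two-sided Wald test. Enrolment is raised to 100, 50 per group, for 20% dropout. These figures concern one overall poor outcome. The Investigations section lists more than 20 single maternal, obstetric, fetal and perinatal outcomes, and none has a stated rate or power.

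**The concern.** An aim of evaluating an effect needs an estimate of that effect and a statement of its precision. Two percentages and a p-value do not say directly how large the effect is, and they do not say which effects the data exclude. The odds ratio that sized the study is not carried into the analysis.

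This matters most where events are few. The list includes obstetric shock, stillbirth, meconium aspiration and neonatal death. If such outcomes occur in only a few women, a p-value above 0.05 is the likely result even when older women have a much higher risk. The table would then look the same whether age truly makes little difference or the study was too small to tell. A confidence interval separates these two situations.

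**Working it through.** **Step 1: reproduce the plan's own figure.** Inputs from the Sample size section: n = 40 per group, 20% versus 60%, two-sided 0.05, Wald test on the log odds ratio.

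- Odds ratio = (0.6/0.4)/(0.2/0.8) = 6.0.
- SE = √[1/(40×0.2×0.8) + 1/(40×0.6×0.4)] = √(0.1563 + 0.1042) = 0.510.
- Power = Φ(ln 6/0.510 − 1.96) = Φ(1.55) = 0.94, as stated.
- Enrolment = 80/(1 − 0.20) = 100, as stated.
- The chi-square test that the analysis section suggests has power 0.97 for the same rates.

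**Step 2: chi-square power for single outcomes.** Control risks are assumed, because the documents give none. With p̄ the mean of the two risks:

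power = Φ{[|p₂ − p₁| − 1.96√(2p̄(1 − p̄)/n)] / √[p₁(1 − p₁)/n + p₂(1 − p₂)/n]}

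For example, 20% versus 40% at n = 40: (0.20 − 1.96×0.1025)/0.100 = −0.008, so power is 0.497.

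| Assumed control risk | Doubling, 40/group | Tripling, 40/group | Doubling, 50/group | Tripling, 50/group |
|---|---|---|---|---|
| 5% | 13% | 32% | 16% | 38% |
| 10% | 24% | 61% | 29% | 71% |
| 15% | 36% | 85% | 43% | 92% |
| 20% | 50% | 97% | 59% | 99% |

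At 40 per group, a tripling from 2% to 6% has 15% power and a doubling from 30% to 60% has 78%. Exact enumeration of the Pearson chi-square test at 40 per group gives similar values: 11% for 2% versus 6%, 15% for 5% versus 10%, 25% for 10% versus 20%, 50% for 20% versus 40%, and 63% for 10% versus 30%.

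Stepping the control risk by half a percentage point, power at 40 per group first reaches 50% at 20.5% for a doubling and at 8.5% for a tripling. It reaches 80% at about 31% and 14%.

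**Step 3: what an interval adds.** Illustrative counts, older versus younger, 40 per group. Intervals are by the log method for the risk ratio and Newcombe for the difference.

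- 3 versus 1: p = 0.30. SE of the log ratio = √(1/3 − 1/40 + 1/1 − 1/40) = 1.133. Risk ratio 3.0, 95% CI 3.0×exp(±1.96×1.133) = 0.33 to 27.6. Difference 5 points (−6.5 to 17.5).
- 8 versus 4: p = 0.21. Risk ratio 2.0 (0.65 to 6.1). Difference 10 points (−6.1 to 25.9).
- No events in 40: exact upper 97.5% limit = 1 − 0.025^(1/40) = 8.8%. With 50 women it is 7.1%.

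In each of the two comparisons the chi-square result is non-significant, while the interval includes both no difference and a several-fold increase.

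**The case against.** The best defence is that the section is less bare than it looks. Chi-square is only a suggested test, quantitative data do get summary measures, and a reader can derive a risk ratio and its interval from the counts. The logistic model in the Sample size section would also yield an odds ratio. Each statement is true, but none amounts to a plan. The analysis section names no effect measure, does not carry the logistic model forward, and leaves precision for the reader to work out.

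The other objections concern scope, and they stand. Three stronger readings are tempting:

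- A reader might infer that a tripling of risk will usually be missed. The documents contradict this as a general claim: the design target is itself a tripling, with 94% stated power. A tripling from 10% already has 61% to 63% power, and from 15% it has 85%. The claim is limited to uncommon outcomes.
- A reader might infer that nearly all listed outcomes are uncommon. No control rate is given for any of them, and the list also contains cesarean delivery, anemia, NICU admission and preterm birth, which nothing in the documents shows to be rare.
- A reader might infer that the investigators will take p > 0.05 as showing no effect of age. No section says so. It is a foreseeable misreading that the plan does nothing to prevent, and not a stated intention.

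Finally, 40 per group is the number after the full assumed dropout. With all 50 retained, power is higher, for example 59% for 20% versus 40%, but still low for uncommon outcomes.

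**Conclusion.** The point holds in a limited form. The plan sets out to evaluate an effect and was sized on an odds ratio, but it specifies no effect estimate and no confidence interval for its categorical outcomes. This gap can be read directly from the text and needs no assumption about rates.

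Its consequence depends on control risk, which is assumed. At 40 per group, a doubling has 50% power or less up to about 20% control risk, and a tripling has under 50% only below about 8.5%. For single outcomes in those ranges, a non-significant chi-square would say little about effect size, and the planned output would not make that visible. The overall poor outcome at its assumed 20% and 60% is adequately powered. For that outcome the gap is only the missing estimate and interval.

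**What to change.** Amend the Statistical analysis section as follows:

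1. For each binary outcome, report the risk difference and risk ratio, older versus younger, with 95% confidence intervals. Use Newcombe or Miettinen-Nurminen for the difference and a score interval for the ratio. Give an exact upper limit where a group has no events. The p-value comes second.
2. For the overall poor outcome, also report the odds ratio with its 95% confidence interval from the logistic model used in the Sample size section.
3. State that a non-significant result is not evidence of no effect and will be interpreted from the interval.

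I would not add a rule that declares no effect once the interval excludes a doubling. It would let a 1.9-fold increase be called no effect, and it could seldom be met. With equal observed risks at 40 per group, the upper limit of the risk ratio (log method) is exp(1.96×√[2(1/4 − 1/40)]) = 3.7 at 10% risk. The same formula gives 2.4 at 20%, and the limit falls below 2 only near 30%. Nor do the documents give a basis for fixing in advance a list of outcomes to leave untested.

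The cost is revised wording and a few table columns, with no extra data or participants. The downside is that rare outcomes will show very wide intervals, which is an honest picture of what a study of this size can say about them.

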**2021**

## Introduction

Advanced maternal age (AMA) is mostly defined as a pregnancy in women  $\geq 35$  years of age or more during their pregnancy or time of delivery (1). It grows trending in high-income countries, which is most commonly seen in older primigravida women who delay child bearing by life style choice or due to underlying subfertility, but also includes multiparous women continuing childbearing. Approximately 18% of all united states birth in 2018 were to women with advanced maternal age compare with approximately 5% before, much of this shift due to delayed first births, the rate of first births increased seven-fold among women aged 35 to 39 y and five-fold among women aged 40 to 44 y between 1985 and 2018 (2).

In England, the incidence of births to women aged 35y increased from 6% to 20% at 2013. Pregnancy at advanced maternal age is associated with different adverse neonatal outcomes. It is associated with stillbirth and also complicated by intrauterine fetal death (IUFD) and neonatal death (3 & 4). Advanced maternal age is reported to be associated with a range of pregnancy complications including: fetal growth restriction (FGR), preeclampsia (PE), placental abruption, pre-term birth (PTB) and stillbirth (5).

Perinatal adverse outcomes like preterm birth, early neonatal death, low birth weight, neonatal intensive care unit (NICU) admission and APGAR score of less than seven at five minutes are significantly associated with pregnancy at advanced maternal age (6). The adverse outcomes result from inadequate cardiovascular adaptation during pregnancy, which impedes the hemodynamic changes for supporting the fetus (7). This may explain occurrence of intrauterine growth restriction and placental abruption at advanced maternal age (8).

Early pregnancy outcomes associated with advanced maternal age include: Ectopic pregnancy which increase a four- to eight-fold in women more 35 years increasing maternal mortality and morbidity (9). Epidemiological studies show an association between advanced maternal and paternal ages and the risk of autism spectrum disorders in the offspring, also advanced maternal age is a risk factor for congenital malformation and Down syndrome (10).

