#### **A. Inclusion criteria:**

- Primigravida Women with singleton pregnancies aged 20 to 34 years in control group and aged 35 y or more in case group, natural conception or with using ART, who seeking for routine antenatal care to the university hospital and who will accept the study protocol.

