#### **B. Exclusion criteria:**

- Patients aged less than 20 y will be excluded from the study.
- Patients with medical disorders (antiphospholipid syndrome, chronic hypertension, pre-existing diabetes, autoimmune diseases, thrombo-embolic disease).
- Multipara.

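### No adjusted analysis is prespecified for the age effect, and the ART versus spontaneous comparison has no stated population or method, so a pooled chi-square would be confounded by age

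*Combined protocol and SAP*

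**What the plan says.** The Aim of work is to "evaluate the effect of advanced maternal age on the outcomes of pregnancy", and the Study Design section describes a prospective cohort, so age group is observed and not assigned.

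The Introduction describes "older primigravida women who delay child bearing by life style choice or due to underlying subfertility". The inclusion criteria admit "natural conception or with using ART". Restriction by design covers parity, multiple pregnancy and the listed disorders ("antiphospholipid syndrome, chronic hypertension, pre-existing diabetes, autoimmune diseases, thrombo-embolic disease"). It does not cover mode of conception.

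The Statistical analysis section gives the software, descriptive summaries, a normality test and this sentence: "The appropriate statistical test will be applied according to data type with the following suggested tests: Chi-Square for categorical variable". It names no covariate, stratification, regression model, effect measure or confidence interval.

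A regression appears only in the Sample size section: "A logistic regression of a binary response variable (Y) on a binary independent variable (X) with a sample size (N) of 80 observations". Its single predictor is age group. The same section says that the older group "will be also divided into 2 subgroups: group (1A) aged from 35y to 40 y" (1B being those above 40), and the next bullet reads "We will also compare between those with spontaneous pregnancy and those with ART". That bullet gives no population, outcome or method.

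**The concern.** There are two linked gaps.

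**Age comparison.** A crude comparison of older with younger women mixes age with whatever travels with it. The protocol itself points to one such factor, subfertility and hence ART. The plan does not say whether the age effect is meant to include what goes with conception mode or to be separate from it. A rule that picks tests by data type does not settle that, and it leaves adjustment to be decided after the results are known.

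**ART comparison.** The plan expects a poor outcome three times as often in older women (60% against 20%). If ART is also more common in older women, a comparison pooled over both age groups partly measures age. If it is run only in women aged 35 or more, that problem is largely removed. The text allows either reading.

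**Working it through.** **The plan's own figure.** Rates of 0.20 and 0.60 with 40 per group give OR = (0.6/0.4)/(0.2/0.8) = 6.0. SE of the log OR = √[1/(40×0.2×0.8) + 1/(40×0.6×0.4)] = 0.510. Wald power = Φ(1.792/0.510 − 1.96) = 0.940. The stated 94% is reproduced, for the unadjusted contrast. Enrolment is 80/(1 − 0.20) = 100, as stated.

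**Assumptions.** The documents give neither the share of women using ART nor an ART effect. I take ART shares (older/younger) from 10%/5% to 50%/5% and, where an ART effect is needed, an OR of 2 to 3.

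**1. ART comparison pooled over age, no true ART effect.** Risk is 60% in every older woman and 20% in every younger one.
- At 50%/5%: 20 + 2 = 22 ART women with 20×0.6 + 2×0.2 = 12.4 expected events (0.564). The other 58 have 32 − 12.4 = 19.6 (0.338). Crude OR = 2.53.
- At 10%/5%: 4 + 2 = 6 ART women with 2.8 events (0.467). The other 74 have 29.2 (0.395). Crude OR = 1.34.

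Simulated rejection at the 5% level (40,000 replicates, 40 per group):

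| ART share, older/younger | Crude ART OR | Pooled chi-square | Mantel-Haenszel by age |
|---|---|---|---|
| 10%/5% | 1.34 | 6–7% | about 5% |
| 15%/5% | 1.57 | 10% | about 5% |
| 30%/10% | 1.67 | 16% | about 5% |
| 30%/5% | 2.02 | 23% | about 5% |
| 50%/10% | 2.19 | 37% | about 5% |
| 50%/5% | 2.53 | 46% | about 5% |

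Run in the older group only, the chi-square rejects in about 5%, or slightly less when very few women used ART.

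**2. Age comparison with no direct age effect.** Take 20% risk without ART.
- ART OR 2 gives an ART risk of 0.333. At 10%/5% the group risks are 0.213 and 0.207, crude age OR 1.04.
- ART OR 3 gives an ART risk of 0.429. At 50%/5% they are 0.314 and 0.211, crude age OR 1.71.

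**3. The planned effect after adjustment.** Suppose 20% and 60% are crude rates and the ART OR is 2 to 3. Solving for the ART-adjusted age OR over shares of 30–50% and 5–10% gives 5.35 (ART OR 2, 30%/10%) down to 3.84 (ART OR 3, 50%/5%).

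**4. Power of the adjusted age test, model with age and ART only.** Take an adjusted OR of 6 and, for simplicity, no ART effect. Within each ART stratum let A and B be n×p×(1 − p) for older and younger women. The information is the sum over strata of A×B/(A + B).
- At 10%/5%: 8.64×6.08/14.72 + 0.96×0.32/1.28 = 3.81, SE 0.512, power 94%.
- At 50%/5%: 4.8×6.08/10.88 + 4.8×0.32/5.12 = 2.98, SE 0.579, power 87%.
- In the setting of step 3 it is 90% down to 66%.

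**5. Precision of an age-adjusted ART effect, no ART effect.** Information = Σ p(1 − p)×n(ART)×n(spontaneous)/40 over age groups.
- At 50%/10%: 0.24×20×20/40 + 0.16×4×36/40 = 2.98, SE 0.580. The 95% CI runs exp(1.96×0.580) = 3.1-fold either side.
- At 30%/5%: 2.016 + 0.304 = 2.32, SE 0.657, 3.6-fold.
- At 10%/5%: 0.864 + 0.304 = 1.17, SE 0.925, 6.1-fold.

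**6. Model size.** Expected events are 40×0.2 + 40×0.6 = 32, so three terms have 32/3 = 10.7 each.

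**The case against.** The wording is permissive. Chi-square is only suggested, other tests are not excluded, and the sample-size text already thinks in terms of a logistic OR. That stands as a reading, so the plan cannot be said to rule out adjustment. But it specifies none.

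A reader might infer that the ART comparison is biased as planned. The documents do not support that. Its bullet comes straight after the split of the older group and may mean that group only, in which case there is no inflation. The size under pooling also rests on assumed shares. This is routine antenatal care, and at 10–15% against 5% false rejection is only about 6–10%.

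A reader might also infer that ART accounts for the age effect, or that the crude OR is simply wrong. Neither follows. On the shares in step 3 the adjusted OR stays at 3.8 or above, and a crude contrast is a legitimate answer to a total-effect question if ART lies on the path from age. Nor can one say that the crude OR is the total effect and the adjusted OR the direct effect. The Introduction gives subfertility as a reason for late childbearing, which would make it a common cause of older age and ART, and so a confounder. ORs are also non-collapsible, so crude and adjusted values can differ without confounding.

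**Conclusion.** The concern holds as a gap in prespecification with a real consequence. The plan asks for an effect of age, admits ART in both groups, and names no analysis that could separate the two. The direction of the ART problem needs only two conditions: both age groups are pooled without adjustment, and ART is more common in older women. Its size, an OR of about 1.3 to 2.5 and false rejection of about 6% to 46%, depends on shares that the documents do not give. The crude age OR of about 1.04 to 1.7 with no direct age effect is bias only so far as ART or the underlying subfertility is a confounder. The 94% power is correct for the unadjusted contrast. This should be fixed, but it does not prevent the study from proceeding.

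**What to change.** **Statistical analysis section**
- Add a logistic regression of the overall poor outcome on age group, adjusted for mode of conception, with BMI as a secondary covariate. The outcome must first be defined. State the visit at which BMI is taken, since the Clinical examination section does not.
- Report crude and adjusted ORs with 95% CIs, and state in advance which one answers the aim. Note that the interpretation depends on whether ART or subfertility is a confounder or lies on the path from age, and that ORs are non-collapsible.
- Do not adjust for complications that arise in pregnancy.
- Keep the model to these terms, given 32 expected events. Describe education and special habits by group.

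**Sample size section**
- State whether the ART comparison covers both age groups or the older group only. If both, stratify by or adjust for age group. Label it exploratory, given the wide intervals in step 5.
- State that 94% power applies to the unadjusted contrast.

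**Cost.** No new data are needed: age and BMI are recorded, and conception mode must be known for the planned comparison. Intervals will be wider. With age and ART only and an adjusted OR of 6, power at 80 evaluable women is about 87–94% on the assumed shares, and slightly lower with BMI. It is about 66–90% if 20% and 60% are crude rates, the ART OR is 2 to 3 and the shares are 30–50% and 5–10%. Enrolment of 100 need not change.

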### **III. Investigations:**

- All pregnant women will undergo routine investigations at the first antenatal visit which include: CBC, RH grouping, blood grouping, urine analysis, fasting and postprandial blood glucose.

-All pregnant women will be screened for gestational diabetes mellitus (GDM) with a 50-g oral glucose challenge test between 24 and 28 weeks of gestation. Women with abnormal glucose challenge test (140 mg/dL) will undergo a 3-hour oral glucose tolerance test with a 100-g oral glucose load. The diagnosis of GDM will be made when levels of blood glucose are fasting plasma glucose above 95 mg/dL, 1 hour postprandial above 130-140 mg/dL, and 2 hours postprandial above 120mg/dL according to The American College of Obstetricians and Gynecologists (ACOG) recommendations (17).

- All pregnant women will undergo a monthly ultrasound examination until delivery.

- All obstetrical and clinical data will be recorded and collected in an appropriate database.

-Obstetric outcomes will be recorded regarding pregnancy induced hypertension, gestational diabetes mellitus (GDM), anemia, antepartum hemorrhage, oligohydraminos or polyhydraminos, obtetretic shock and intrapartum hemorrhage.

-Maternal outcomes will be recorded regarding mode of delivery “cesarean or vaginal delivery”, premature rupture of membranes, preterm birth which is defined as delivery of an infant before 37 weeks of gestation and will be classified into late preterm (from 34 to less than 37 weeks of gestation) and early preterm birth (delivery from 28 to 34 weeks of gestation), obstructed labor and prolonged labor.

-Fetal outcomes will be recorded regarding congenital malformations, intrauterine growth restriction, intrauterine fetal death and stillbirth.

- Perinatal outcomes will be recorded regarding birth weight which will be classified into low birth weight (less than 2500 g), very low birth weight (less than 1500 g) and macrosomia (more than 4000 g), birth asphyxia, meconium aspiration syndrome, NICU admission, neonatal hypoglycemia, Hyperbilirubinemia, 5-Min Apgar score less than 7 and neonatal death.

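### Does suggesting only chi-square, with no small-count rule, put the over-40 and ART comparisons at risk of false positives?

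*Combined protocol and SAP*

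**What the plan says.** The Statistical analysis section has one sentence on choosing tests: "The appropriate statistical test will be applied according to data type with the following suggested tests: Chi-Square for categorical variable". It mentions no expected-count threshold, exact test or continuity correction. It also does not say that the uncorrected Pearson statistic will be used.

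The Sample size section sets up the main comparison of 50 older and 50 younger women and then adds two more. Within the older women it defines "group (1A) aged from 35y to 40 y, the group (1B) aged above 40 y and we will compare between the outcomes". For mode of conception it says "We will also compare between those with spontaneous pregnancy and those with ART". It states no size for the over-40 group or the ART group.

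The outcomes listed under III. Investigations include some that could produce very few events in 100 women, such as "intrauterine fetal death and stillbirth" and "5-Min Apgar score less than 7 and neonatal death". The documents give no expected rates for them.

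The power statement concerns only the main comparison on an overall poor outcome: the design "achieves 94% power at a 0.050 significance level", and "A two-sided Wald test is used".

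**The concern.** Pearson's chi-square relies on a large-sample approximation that fails when expected counts are well below 5. The two added comparisons could produce such tables, because the over-40 and ART groups may be small and some outcomes are rare. Choosing the test by data type alone takes no account of cell counts. Read literally, the plan could let one stillbirth or neonatal death in a small over-40 or ART group be reported as a statistically significant effect of age or of ART. The choice between chi-square and an exact test could also be made after the data are seen.

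**Working it through.** **Inputs.** From the Sample size section: 50 older and 50 younger women enrolled, 40 and 40 evaluable after 20% dropout, two-sided 0.05, and poor-outcome rates of 0.20 versus 0.60. The subgroup splits and the rare-event rates are assumptions, so ranges are shown.

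**The plan's own figure.** For a Wald test of the log odds ratio with 40 per group, the expected cell counts are 8, 32, 24 and 16.

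- SE = √(1/8 + 1/32 + 1/24 + 1/16) = 0.510
- Power = Φ(ln 6 / 0.510 − 1.96) = Φ(1.55) = 0.940, which matches "achieves 94% power"
- Enrolment = 80 / (1 − 0.20) = 100, as stated

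**A sole event in the small group.** Suppose *m* of *N* women are in the small group and the only event falls there. The uncorrected statistic reduces to χ² = N(N − m) / [m(N − 1)], and Fisher's two-sided p is m/N when m is less than half of N.

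- N = 50, m = 10: χ² = 50 × 40 / (10 × 49) = 4.08, p = 0.043. Fisher 10/50 = 0.200; Yates-corrected p = 0.449. The smallest expected count is 10 × 1/50 = 0.2.
- N = 50, m = 11: χ² = 50 × 39 / (11 × 49) = 3.62, p = 0.057.
- N = 40 (evaluable older women), m = 8: χ² = 40 × 32 / (8 × 39) = 4.10, p = 0.043. At m = 9, χ² = 3.53, p = 0.060.
- ART versus spontaneous: p falls below 0.05 for m up to 20 of 100 enrolled (p = 0.044), or up to 16 of 80 evaluable (p = 0.044).

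The cutoff for women over 40 is therefore 10 of 50 enrolled, or 8 of 40 evaluable. It applies only when there is no event at 35 to 40. With one event there as well, 1/10 versus 1/40 gives χ² = 50 × (1 × 39 − 9 × 1)² / (10 × 40 × 2 × 48) = 1.17, p = 0.279, and 1/5 versus 1/45 gives p = 0.054.

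**True type I error of the uncorrected test.** All 2×2 tables were enumerated, with the same binomial event rate in both groups.

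| Split | 1% | 2% | 3% | 5% | 10% |
|---|---|---|---|---|---|
| 3 / 47 | 2.9 | 5.5 | 7.3 | 8.6 | 6.1 |
| 5 / 45 | 3.2 | 4.1 | 4.2 | 4.1 | 5.0 |
| 8 / 42 | 5.1 | 6.8 | 6.9 | 5.7 | 3.9 |
| 10 / 40 | 6.5 | 8.8 | 9.1 | 7.8 | 4.5 |
| 11 / 39 | 0.4 | 0.9 | 1.5 | 2.3 | 3.4 |
| 8 / 32 | 5.7 | 8.2 | 9.0 | 8.6 | 6.1 |
| 10 / 30 | 0.3 | 0.9 | 1.5 | 2.3 | 2.8 |
| 20 / 80 | 8.8 | 8.7 | 7.2 | 4.7 | 3.7 |
| 21 / 79 | 1.5 | 3.7 | 4.8 | 4.6 | 3.9 |
| 50 / 50 | 0.2 | 1.3 | 2.8 | 4.3 | 5.1 |

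(Entries are percentages.) Fisher's test at 10/40 gives 0.3%, 0.8%, 1.2%, 1.8% and 2.4%.

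The jump between 10/40 and 11/39 comes from one table. At 10/40 and a 2% rate, the chance of a sole event in the small group is 10 × 0.02 × 0.98⁴⁹ = 7.4%, which is most of the 8.8%. One more woman over 40 takes that table out of the rejection region.

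**Cost of a fixed rule.** At 10/40, power to detect 30% in the small group against 5% in the large group falls from 64% with Pearson to 55% with Fisher. It falls to 39% if outcomes with fewer than 5 events also get no p-value.

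**The case for a change.** The strongest case for a change is that sparse tables are foreseeable and the remedy is short. The plan commits to both extra comparisons, fixes neither subgroup's size, and so cannot rule out the splits at which the error rises to about 9%. The words that allow an exact test do not require one or say when to use it. Even where overall error is near nominal, the p-value for a lone event can mislead: 1/5 versus 0/45 gives Pearson p = 0.0024 against Fisher 0.10.

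The arithmetic stands, and so does the observation that no small-count rule is written down. What does not follow is that the plan prescribes an invalid analysis. It leaves the choice to what is appropriate, and an exact test for expected counts as low as 0.2 is ordinary practice. The example at 10/40 is also the least favourable case, since it is the largest small group at which a lone event crosses 0.05. A stricter rule that withholds p-values below 5 events costs enough power that statisticians could reasonably disagree about it.

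**Conclusion.** No change to the plan is called for. The section leaves a detail unwritten, and its wording lets the analyst supply it sensibly with an exact test for sparse tables.

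The possible harm is limited to two secondary comparisons with no power claim. If uncorrected Pearson were used regardless, the error would reach about 9% at the worst splits (10/40, 8/32 and 20/80), mostly at event rates of 1% to 5%. It stays below 5% at 11/39, 10/30 and 21/79, and is at or below 5.0% at 5/45. In the main comparison the error is 0.2% to 4.3% at rates of 1% to 5%, and 5.1% at 10%.

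This conclusion assumes that the analyst takes the word appropriate at face value. The splits and event rates are illustrative because the documents give neither. A reader of the eventual report should check which test lies behind any subgroup p-value that rests on one or two events.
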